9.2 Sample Size and Randomization

In **Table 8** below we present a range of minimum detectable effect size differences for the primary outcomes of Pain Interference or Function Scores for both the administrative sample (N=84 per clinic) and survey sample (N=42 per clinic) for 16 clinics (8 clinics randomized to each arm) for Aim 1. Sample size calculations for the cluster randomized design were based on the net difference between the two conditions across baseline and 3-months follow-up.⁵⁰ We assumed over time correlations of 0.50 for both patients (based on data from the [name] et al. pilot study³³ and summary data available for Durham VA clinics, intraclass correlation coefficients (ICC) of 0.01, 0.02, and 0.05 to account for clinic clustering, and also adjusted for the potential group-level randomization of up to 4 stratification variables as baseline covariate adjustments where we conservatively assumed no reduction in either group or subject level variance components. For all calculations, the type-I error is 2.5% to account for the multiple primary outcomes and power is conservatively assumed to be 90% to guard against deviations from assumptions. The number needed at baseline (N_b) is based on an attrition rate of 20%. Note in the **below Table 4** that the scenarios above lead to having adequate power to detect a medium effect size for the primary outcomes for both the administrative and survey samples.

Table 8. Minimum detectable effect size differences for 90% power, alpha of 0.025 and ICC of 0.01, 0.02, and 0.05 for administrative outcome (n=84 per clinic) and survey outcome (n=42 per clinic)

Number of clinics per condition	Number of patients per clinic needed at post-intervention follow-up (Total N)	Minimum Detectable Effect Size Difference ICC=0.01	Minimum Detectable Effect Size Difference ICC=0.02	Minimum Detectable Effect Size Difference ICC=0.05	Number of patients per clinic needed at baseline with 20% attrition (Total N_b)
8	42 (N=672)	0.37	0.42	0.55	53 (N_b =848)
8	84 (N=1344)	0.30	0.36	0.50	105 (N_b =1680)

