9.2.1 Treatment Assignment Procedures

In this study, randomization occurs at the clinic (i.e., the cluster) level and we plan on conducting a covariate constrained randomization²⁻⁴ with the following clinic level covariates assessed prior to randomization: 1) average pain scale scores of LBP patients at clinic, 2) average level of opioid exposure of LBP patients at clinic, 3) number of participating primary care providers at clinic, 4) clinic location (main medical center/community clinic) and 5) average age of LBP patients at clinic. These characteristics were chosen to represent factors likely to be associated with baseline differences in patient population that may affect primary outcomes. However, the exact number of covariates we use will depend on the quality and distribution of these covariates across the 16 clinics that we enroll. For example, if all the clinics we enroll are community clinics, then we would drop the clinic location covariate in the randomization.

Currently, throughout the VA, general pain scale scores (rate pain on a scale from 1 to 10) are being collected for all primary care visits and stored in administrative data. Our plan will be to use these data, averaging the pain scale scores of LBP Veterans at each clinic over a 3 to 6-month time period prior to clinic enrollment. For Durham primary care clinics, we found that pain scores were collected at over 95% of primary care visits for lower back pain over a one-year time period. From the [name] et al. pilot study³³ of Veterans with back pain (n=50), we found that correlation of pain scale scores to PROMIS pain interference at baseline was approximately 0.55, a reasonably strong correlation. For the opioid exposure covariate, our plan is to apply the PMC3 opioid exposure definition to LBP patients at clinics over a 3 to 6-month period prior to clinic enrollment and then use the proportion of patients that meet the opioid exposure definition as the average level of opioid exposure for the clinic. The number of participating (referring) providers at a clinic will be used as an indication of size of clinic (volume of patients served). For the age of LBP patients, we will use age that is available in the electronic health record and average the age of Veterans with LBP visits to the clinic over the 3 to 6-month time period prior to clinic enrollment.

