9.3 Definition of Populations

As this is an embedded pragmatic trial, all adult subjects that present to clinics with LBP and are referred to one of the two arms of the trial with initial contact with pain navigator or central delivery for data collection will be eligible for the primary analysis as part of the administrative sample. A subset of these Veterans will be enrolled as research subjects so that more detailed research data can be collected at regular intervals for follow up. For this subgroup, equivalent numbers of Veterans with LBP will be enrolled at each clinic.

The primary analyses will be conducted on an intention-to-treat basis; patients will be analyzed in the group to which they were randomized, regardless of intervention adherence, using all available data. The main conclusions drawn from this trial will be based on the pre-specified hypotheses outlined below and will be tested with two-sided p-values at the standard 0.05 level, except where noted due to multiple primary outcomes. For all study outcomes, we will interpret differences between groups over time with reference to prior literature regarding clinically meaningful changes. Results from exploratory analyses will be interpreted with appropriate consideration for their exploratory nature. Statistical analyses will be performed using the latest release of SAS for Windows (Cary, NC) and R software.

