$\beta_1^*(\text{moderator}) + \beta_2^*(\text{moderator}^*\text{intervention}) + \beta_3^*(\text{followup}) + \beta_4^*(\text{followup}^*\text{intervention}) + \beta_5^*(\text{moderator}^*\text{followup}) + \beta_6^*(\text{moderator}^*\text{intervention}^*\text{followup})$ for clinic i , patient j , at time k . A random effects (clinics and time by clinics) will be included in the model to account for clustering of patients within clinics, as the clinics are the unit of randomization. Differential change in pain interference or function by moderator for the two intervention groups is supported if the coefficient for β_6 is significantly different than zero at the $p=0.025$ level. For the adherence multinomial outcome, we will fit a generalized linear model with a random effect for clinic and cumulative logit link function. As the adherence outcome is potentially a 3-level outcome there will be two interaction terms to examine for moderation effects (e.g. whether the effect of the intervention by chronicity is different for those moderately adherent vs. not adherent and/or those fully adherent vs. not adherent).

Exploratory analyses to identify multidimensional subgroups from combinations of baseline characteristics (e.g. age, sex, opioid use) for treatment moderation of the primary outcomes of pain and function as well as per protocol adherence to treatment.

Patients are likely to vary in treatment response. This variation is known as heterogeneity of treatment effects (HTE). Exploration of HTE has typically focused on one-factor-at-a-time post-hoc subgroup analyses (as described in our planned subgroup analysis); however, it is possible to instead identify multidimensional subgroups exhibiting HTE. In particular, we will apply the data-driven method GUIDE⁶⁶(Generalized, Unbiased, Interaction Detection and Estimation) that can be used for longitudinal outcomes, so can incorporate all follow-up outcomes at 3 and 12-months, as well as multi-response outcomes. GUIDE uses a regression tree algorithm that identifies subgroups with heterogeneous effects and estimates how the treatment effect varies across the subgroups. We will include baseline demographic (e.g. age, sex, race) and clinical characteristics (e.g. LBP chronicity, opioid use, comorbid conditions) that are available from EHR. GUIDE provides bootstrap confidence intervals for the treatment effects of identified nodes and is available via a software package.

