As part of personalized medicine, tailored treatment recommendations are the goal. In this trial, we are offering two different treatments, and we want to explore identifying qualitative interactions that define groups of individuals that have greater improvement with one treatment over the other. We will apply the tree-based method called Qualitative Interaction Trees (QUINT) to identify these subgroups.^{67,68} QUINT is a tree-based clustering method for data obtained from a two-armed trial that identifies three subgroups defined by different baseline characteristics of subjects in the study. QUINT uses a partitioning criterion that is maximized using a sequential partitioning algorithm or a stepwise binary splitting procedure. We will use the R package *quint* and apply to our study data to identify characteristics for Veterans where integrated care pathway treatment results in greater improvement in outcomes than care management pathway, subgroup of Veterans that care management pathway results in greater improvements than integrated care pathway and the subgroup for which improvement does not differ between treatments. We will first construct a summary of each patient's repeated measures profile to characterize the patient's change over time at the primary time point 3-months (i.e., whether or not the patient improved and mean improvement). Empirical Bayes estimates from hierarchical linear models will be used to generate individual-level estimates of mean improvement for each of the primary outcomes. Currently this software only supports continuous outcomes so we would not be able to apply to the multilevel response adherence outcome; however, we will monitor updates for expansion to other distributions of outcomes. Limitation of this methods are that subjects with missing data on any included variables are omitted from the analysis, the effect of clustering within clinics is not addressed, and categorical baseline characteristics of more than two categories cannot be used.

Statistical methods for heterogeneity of treatment effects (HTE) are a rapidly developing field. We will monitor the development of new methods that may be applicable to our study for adapting the analysis plan for this aim, and work closely with the PMC3 Biostatistics Working Group and [name] (an internal advisory member for this proposal) to ensure robustness of our chosen methods.

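### The GUIDE paragraph relies on packaged bootstrap intervals for node treatment effects without naming a resampling unit, clinic adjustment or clustering limitation, although arm is constant within clinic

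*Combined protocol and SAP*

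**What the plan says.** Section 9.2.1 fixes the design: "In this study, randomization occurs at the clinic (i.e., the cluster) level". Section 9.2 plans 16 clinics, eight per arm, and powers the trial with "intraclass correlation coefficients (ICC) of 0.01, 0.02, and 0.05 to account for clinic clustering".

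Section 9.6 follows this through in most places. The Aim 1 model has clinic and time-by-clinic random effects because clinics were randomized. The planned moderator model has the same effects. The binary secondary models adjust for clinic by random effects or conditioning. For QUINT, the plan lists as a limitation that "the effect of clustering within clinics is not addressed".

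For GUIDE, the only statement about inference is "GUIDE provides bootstrap confidence intervals for the treatment effects of identified nodes and is available via a software package". That paragraph has no clinic term, no resampling unit and no limitation. Section 9.3 says in general that exploratory results will be read as exploratory. Section 9.6 adds that new methods for heterogeneous treatment effects will be monitored and taken up with a biostatistics working group. Neither statement mentions clustering in GUIDE.

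**The concern.** Within a GUIDE node, all patients from one clinic are in the same arm. However many patients the node holds, its treatment effect compares at most eight clinic means with eight others. A bootstrap that draws patients independently reproduces the variation between patients but not the variation between clinics. Its interval would then be too narrow for the effect it describes.

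The stake is a within-node claim that one pathway is better than the other. Section 1.2 wants the subgroup work to show which characteristics go with better outcomes in either pathway, and a reader will take a printed 95% interval at face value. Because QUINT carries a clustering warning and GUIDE does not, a reader could conclude that GUIDE is free of the problem.

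**Working it through.** **Inputs from the documents.** Eight clinics per arm; ICC 0.01, 0.02, 0.05; over-time correlation 0.50; alpha 0.025; power 90% (section 9.2). Testing is two-sided (section 9.3). The correlation sentence, "We assumed over time correlations of 0.50 for both patients", does not name a second level; I take it to apply to patients and clinics alike.

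**Inputs assumed.** The documents give no node sizes. I use m = 21 per clinic (the effective size behind Table 9), 42 (half of the 84 followed up per clinic) and 10. Patient-level resampling is also an assumption.

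**1. Reproduce the plan's own figures.** With design effect DEFF = 1 + (m − 1) × ICC,

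MDD = [t(0.9875; df) + t(0.90; df)] × √[2 × 2 × (1 − 0.50) × DEFF / (8m)].

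With df = 14 − 5 = 9, the bracket is 2.685 + 1.383 = 4.068. For m = 84 and ICC 0.01, DEFF = 1.83 and MDD = 4.068 × √(2 × 1.83 / 672) = 0.300.

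| m per clinic | Computed, ICC 0.01/0.02/0.05 | Stated |
|---|---|---|
| 84 (Table 8) | 0.300 / 0.362 / 0.504 | 0.30 / 0.36 / 0.50 |
| 42 (Table 8) | 0.373 / 0.423 / 0.548 | 0.37 / 0.42 / 0.55 |
| 21 (Table 9) | 0.486 / 0.525 / 0.628 | 0.48 / 0.53 / 0.63 |

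All agree within 3%, so this variance structure matches the plan's own power calculation.

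**2. Coverage if patients are resampled.** Naive SE / true SE = 1/√DEFF, and coverage of a nominal 95% interval = 2Φ(1.96/√DEFF) − 1. For m = 21 and ICC 0.05, DEFF = 1 + 20 × 0.05 = 2.00, the SE ratio is 0.71 and coverage is 2Φ(1.386) − 1 = 83.4%.

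| m per clinic | DEFF, ICC 0.01/0.02/0.05 | Naive width as % of required | Coverage |
|---|---|---|---|
| 10 | 1.09 / 1.18 / 1.45 | 96 / 92 / 83 | 94.0% / 92.9% / 89.6% |
| 21 | 1.20 / 1.40 / 2.00 | 91 / 85 / 71 | 92.6% / 90.2% / 83.4% |
| 42 | 1.41 / 1.82 / 3.05 | 84 / 74 / 57 | 90.1% / 85.4% / 73.8% |

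A simulation (1,500 trials, 300 bootstrap draws, 8 + 8 clinics, equal node sizes, no tree selection) gave 91.1%/89.4%/81.8% for m = 21 and 90.2%/85.1%/70.0% for m = 42. With ICC 0 it gave 93–94%.

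**3. Sensitivity to the clinic-level over-time correlation r.** Taking within-clinic variance as the base, DEFF = 1 + m × ICC × (1 − r) / [(1 − ICC) × 0.5]. For m = 21, r = 0.5 gives 1.21/1.43/2.11, close to step 2. With r = 0.8 it is 1.09/1.17/1.44 (coverage about 94%/93%/90%). With r = 0.9 it is 1.04/1.09/1.22.

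**4. Differences between nodes.** If a clinic's deviation is shared by its patients in two nodes, it cancels from the difference between the two node effects. The true variance is then (1 − ICC) times the naive one, so coverage is 2Φ(1.96/√(1 − ICC)) − 1 = 95.1%/95.2%/95.6%.

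**5. Candidate remedies, same simulation.** A t interval on clinic means with 14 df covered 94–96%. A plain percentile bootstrap of 8 + 8 clinics covered only about 89–92%. Relative to the patient-level interval, the t interval is wider by √DEFF × 2.145/1.96: 1.20/1.29/1.55 for m = 21 and 1.30/1.48/1.91 for m = 42.

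**The case against.** The strongest reply is that the documents never state how GUIDE resamples, so one cannot say that its intervals are too narrow. That stands: what is documented is an unspecified unit and a missing limitation, and the narrowness is conditional on patient resampling.

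Three stronger readings are tempting and are not supported:

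- A reader might infer that chance differences between clinics would appear as spurious heterogeneity. GUIDE's nodes are built from patient characteristics, so a clinic normally contributes to several nodes and a shared clinic effect largely cancels (step 4). False heterogeneity would need clinic effects that vary with the splitting characteristics, or nodes concentrated in particular clinics.
- A reader might infer that these intervals decide which subgroups are reported. Section 9.6 says that the software provides them. It sets no decision rule and does not commit to reporting them; the tree algorithm identifies the subgroups.
- A reader might apply the formula to 84 per clinic and quote far lower coverage. That is the whole follow-up sample, a tree with no split.

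The defence can also say that the analysis is exploratory, that methods will be monitored, and that the planned moderator tests already carry clinic effects. This limits the consequences but does not correct an interval. QUINT is equally exploratory, and there the plan thought the clustering limitation worth stating.

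**Conclusion.** The point holds as a gap in the specification with a conditional statistical consequence. The plan treats clinic variance as necessary in its other models and discloses its absence in QUINT, but is silent for GUIDE. If patients are resampled, an interval for a pathway effect within a node would be too narrow: slightly so for small nodes at ICC 0.01, and seriously so for a node of 42 per clinic at ICC 0.05.

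The size rests on assumed node sizes, on the plan's ICCs, and on a clinic-level over-time correlation of 0.50. A higher correlation shrinks the loss without reversing it. None of the figures includes the further effect of choosing nodes from the data. The change is worth making because it is cheap and the output could be over-read.

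**What to change.** 1. Keep GUIDE for finding the splits. Report each node's ICP-versus-CCP effect from the Aim 1 mixed model, with clinic and time-by-clinic random effects and clinic-level degrees of freedom: 14, less one for each clinic-level covariate kept (9 if all five are).
2. Alternatively, resample whole clinics within arm, rerun the tree in each resample, and add a small-cluster correction. Resampling clinics alone is not enough with 8 + 8.
3. State that a mixed-model refit does not correct for nodes having been chosen from the same data.
4. State GUIDE's resampling unit, extend the QUINT clustering limitation to GUIDE, and label any packaged intervals as descriptive.

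No new data are needed. The cost is a little scripting and wider intervals, by the factors in step 5 if 14 df are used and somewhat more with fewer df.

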9.6 Data Analyses

Aim 1 Analyses

The primary outcomes are continuous and will be ascertained at the planned baseline and follow-up assessment (3 months) from administrative data collected from the EHR on all eligible LBP Veterans presenting at participating clinics. Changes in pain interference and/or physical function scores will be estimated and the primary hypotheses tested via hierarchical linear mixed-effects models with patients nested within clinics and baseline and 3 month values in the response vector.⁵⁵ Hierarchical linear models are a flexible and powerful analytic tool for clustered longitudinal continuous outcomes. The fixed-effect portion of the model will have the form: $Y_{ijk} = \beta_0 + \beta_1 * (followup) + \beta_2 * (followup * intervention)$ for clinic i , patient j , at time k . Random effects (clinics and time by clinics) will be included in the model to account for clustering of patients within clinics as the clinics are the unit of randomization, random effects will also be included to account for the within-patient correlation between repeated measures over time. We will assess the best fitting random effects structure by fitting a variety of random coefficient models (e.g., random intercept only, random intercept and linear slope) and assess using Akaike Information Criteria (AIC) model selection criteria.^{56,57} The predictors in the model will include a time effect and indicator variables for treatment interacting with the time effect. The intraclass correlation capturing the relationship of outcomes between patients seen at the same clinic is accounted for via the random effects for the clinics and time by clinics, which are assumed to be normally distributed. The model will be fit in the SAS procedure PROC MIXED using full likelihood approximation and the hypotheses will be tested by whether the estimated coefficient β_2 is positive and significantly different than 0 at the 0.025 level due to 2 primary outcome variables. We will include covariates used in the covariate constrained randomization⁴ (5 potential variables; average pain scores, clinic location (main medical center/community clinic), number of participating primary care providers, average level of opioid exposure of LBP patients at clinic, and average age of LBP patients at clinic) in our primary model as well as a limited number of patient-level covariates that are readily available in the EHR (age, gender, race and a comorbidity measure). While we have procedures in place to monitor timing of the 3-month follow-up assessment in the EHR, if we have a significant number of assessments outside the 1-month window for the 3-month assessment that are dropped from the primary analysis, we will conduct a sensitivity analysis including the assessments outside the window and estimating a 3-month treatment effect from this model.

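### QUINT is to be run on empirical Bayes improvement from a two-occasion model; depending on a random-effects structure left to AIC, that score carries no patient-level signal, an arbitrary amount, or a shrunken one

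*Combined protocol and SAP*

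**What the plan says.** In Section 9.6, the QUINT paragraphs first summarise each patient's repeated measures to "characterize the patient's change over time at the primary time point 3-months". They continue: "Empirical Bayes estimates from hierarchical linear models will be used to generate individual-level estimates of mean improvement for each of the primary outcomes". QUINT is to split patients on these values into those who do better on the ICP, those who do better on the CCP, and those for whom the pathways do not differ. Among the stated limitations, patients with missing data are dropped and "the effect of clustering within clinics is not addressed". Nothing is said about how much patient-level information the estimates contain.

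Section 9.5.1 defines the primary outcomes as EHR scores. The Aim 1 part of Section 9.6 models them "with patients nested within clinics and baseline and 3 month values in the response vector". Change enters the fixed part only through follow-up and follow-up by intervention. At clinic level, "Random effects (clinics and time by clinics) will be included in the model". At patient level, "random effects will also be included to account for the within-patient correlation between repeated measures over time"; their form is left to AIC after "fitting a variety of random coefficient models (e.g., random intercept only, random intercept and linear slope").

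**The concern.** An empirical Bayes (EB) estimate of change contains only as much patient-specific change as the model gives it. With two measurements per patient, a model has little room to separate a patient's own change from residual error.

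Two things are at stake. If the score is the same for everyone in a clinic, any split on a patient characteristic reflects only the mix of patients across clinics, which is the clustering QUINT ignores. A tree with no splits would then be read as evidence that there are no subgroups. If the score does vary but is shrunk around the arm effect, a subgroup that truly does better on the other pathway can appear merely to benefit less. Finding such subgroups is the purpose of the analysis.

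**Working it through.** **Inputs.** From Section 9.2 and Table 8: 8 clinics per arm, 84 patients per clinic at follow-up (16 × 84 = 1,344), over-time correlation r = 0.50, ICC 0.01 to 0.05. The plan gives no figure for QUINT, so Table 8 serves to confirm the covariance assumptions:

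MDE = (t(0.9875; 9) + t(0.90; 9)) × √{4[(1−ICC)(1−r) + m·ICC·(1−r)]/(m·g)}

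Here m = 84, g = 8, df = 14 − 5 = 9, and variances are equal at both times. The t values sum to 2.685 + 1.383 = 4.068. The results are 0.300, 0.362 and 0.504, against 0.30, 0.36 and 0.50 in Table 8.

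Two assumptions are not in the documents: the ratio q of follow-up to baseline variance (0.8 to 1.5), and a 0.5 SD interaction.

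**Notation.** Follow-up is coded 0/1. Patient-level baseline variance is v0, follow-up variance v1 and covariance c. A patient's deviations from the model mean are d0 and d1.

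**1. Patient intercept only.** Predicted follow-up minus predicted baseline is β1 + β2·arm + (clinic time effect). The patient intercept and the patient covariates, which are listed without a time interaction, cancel. In simulated trials with the plan's clinic terms (16 × 84, ICC 0.02), the within-clinic SD of EB change was 0.000 in every run. For observed change it was about 1.0 to 1.16 when an interaction was present.

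**2. Correlated intercept and slope plus residual.** The moments are v0 = s0 + e, c = s0 + s01 and v1 = s0 + 2·s01 + s1 + e: four unknowns and three equations. With v0 = v1 = 1 and c = 0.5, every residual variance e from 0 to 0.5 gives the same likelihood. The EB slope is (1 − 2e) times the patient's deviation in observed change: 100% at e = 0, 50% at e = 0.25, 0% at e = 0.5.

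**3. Independent intercept and slope.** Three unknowns and three equations, so identified, with s1 = v1 − v0. Then

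EB slope = [s1/(v1 − c²/v0)] × [d1 − (c/v0)·d0]

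This is a shrunken multiple of the baseline-adjusted 3-month score, and it is zero for everyone if v1 does not exceed v0.

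**Size under structure 3.** Let a balanced binary factor shift the treatment effect by ±0.5 SD around its mean. This adds 0.25 to follow-up variance in the one arm where it acts, or 0.125 averaged over both arms. With v0 = 1, c = 0.5√q and v1 = q + 0.125, where q is the ratio before this addition, the share of the interaction kept is

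k = max(0, q + 0.125 − 1)/(0.75q + 0.125)

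For true subgroup effects of +0.8 and −0.2 SD (mean 0.30, the smallest Table 8 effect for 84 per clinic), the EB effects are 0.30 ± 0.5k.

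| q | k | Share kept, 16-clinic simulation | AIC chose slope | EB subgroup effects | Sign reversal in EB score |
|---|---|---|---|---|---|
| 0.8 | 0 | none | 0% | +0.30 / +0.30 | 0% |
| 1.0 | 0.125/0.875 = 0.14 | about 16% | 75–88% | +0.37 / +0.23 | 0% |
| 1.25 | 0.375/1.0625 = 0.35 | about 35% | 100% | +0.48 / +0.12 | 1% |
| 1.5 | 0.625/1.25 = 0.50 | about 50% | 100% | +0.55 / +0.05 | 23.5% |

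The third and fourth columns come from 40 simulated trials per setting. The last comes from 200 per setting without clinic effects, whose mean EB effects agreed with the formula to about 0.01. In those same trials, observed change showed the reversal in at least 98.5%. With no interaction and equal variances, AIC chose the slope model in only 3–10% of trials. QUINT itself was not run; these results describe its input.

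**The case against.** A reader might infer that two occasions always make EB change constant within a clinic, so that QUINT cannot find anything. The documents do not support that. Section 9.6 also allows a patient slope and does not require it to be correlated with the intercept. The independent form is identified, and AIC usually chose it when an interaction was present and follow-up variance was not smaller than baseline variance.

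It is also fair to say that shrinkage scales signal and noise together. At q = 1, the ±0.5 SD shift divided by the SD of the score is 0.5/√0.875 = 0.53 for the EB score and 0.5/√(1.125 + 1 − 1) = 0.47 for observed change. Within an arm, then, the EB score ranks patients at least as well. This stands, and it is a reason to consider the baseline-adjusted score. It does not rescue the sign reversals, because the arm effect is not shrunk with the deviations. It also fails when follow-up variance is below baseline variance.

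The QUINT text does not name its source model, and the survey has five occasions. But it refers to the primary outcomes at 3 months, which Section 9.5.1 places in the EHR. Table 4 shows additional PROMIS scores at ICP physical therapy visits. The Aim 1 model does not use them, and the CCP update call in Table 5 records none.

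Finally, the analysis is labelled exploratory, Section 9.3 promises cautious interpretation of such results, and Section 9.6 leaves room to adapt the methods for this aim. All of this stands and limits the seriousness.

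**Conclusion.** The point holds in this form: the plan does not fix a patient-level structure under which EB change is both identified and faithful to each patient's change. With an intercept only, it is constant within clinic. With a correlated slope, it is undefined. With an independent slope, it ranges from zero to a shrunken version of the baseline-adjusted score: on the raw scale, none of a 0.5 SD interaction is kept at a variance ratio of 0.8 and roughly 16% to 50% at 1.0 to 1.5. The algebra for the first two structures needs no outside figure. The range for the third rests on the assumed variance ratio and interaction size and on r = 0.50. The consequence is confined to the QUINT results. The primary comparison and the planned moderator tests do not use these estimates.

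**What to change.** In the QUINT part of Section 9.6, replace the EB estimate with each patient's observed baseline-to-3-month change in the EHR score, or with the baseline-adjusted 3-month score, naming one in advance. Use patients in the administrative sample who have a 3-month value, which agrees with the stated omission of patients with missing data. Reserve EB slopes for the survey sample, where five occasions can support them.

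Two sensitivity analyses are optional. One subtracts each clinic's deviation from its arm mean before running QUINT. The other uses multiple imputation; its model should then contain treatment-by-covariate terms, so that imputed values do not dilute the subgroups, and a rule for combining differing trees is needed.

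The cost is a change of SAP wording and a simpler computation. Observed change is noisier than a model prediction. Patients without a 3-month score are excluded, about 1,680 − 1,344 = 336 at the planned 20% attrition. The acknowledged limitation on clustering remains.
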